## 6.6 Concomitant Medication

Medications will be allowed and carefully monitored during the study by the Investigator or designee. The Investigator or designee is responsible for the medical care including medication of the patients during their participation in the study. Any use of concomitant medication must be fully documented in the source document and transcribed into the CRF.

Records of medication taken include the drug name (preferably both generic and trade name), route of administration (*e.g.*, oral, intravenous), total daily dose/unit (*e.g.*, expressed in mg, mL or IU), indication, the start and if applicable, the stop date (day, month and year). Any therapy changes (including changes of regimen) during the study have to be documented. Any concomitant medication that is still being taken by the patient at the EOS will be recorded in the CRF.

Treatment of periodontitis with antibiotics or bisphosphonates should be avoided as much as possible during the study. If required for the periodontal treatment, systemic or topical (in the mouth) antibiotics should not be given for more than 5 consecutive days and will be recorded

### Confidentiality Statement

---

Data and information contained in this document are considered to constitute trade secrets and confidential commercial information, and the legal protections provided to such trade secrets and confidential information are hereby claimed under the applicable provisions of applicable law. No part of this document may be publicly disclosed without the written consent of Philip Morris Products S.A.

---

as concomitant medication, but this will not necessarily be a reason to discontinue the patient from the study (section 5.2). If required, systemic antibiotics for other medical conditions should ideally not be taken for more than 2 consecutive weeks. Systemic steroidal or non-steroidal anti-inflammatory drugs should not be given for more than 6 consecutive days. Anti-coagulants for any medical condition should also be avoided as much as possible. However all treatment needed must be in the best interest of the patient and would not lead to discontinuation.

## **6.7 Concomitant Therapeutic Procedures**

Any concomitant therapeutic procedure (e.g. tooth extraction due to cavity or due to worsening of periodontitis, appendicectomy), which is not part of study procedures (as described in Section 7), will be fully documented in the source document and transcribed into the CRF. All medications used during these concomitant procedures will also be captured in the source document and reported as concomitant medication in the CRF.

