### Unscheduled visits

As a general rule, procedures requested in the protocol should be performed according to the visit schedule. However, as this study is focused on treating patients, there may be a number of reasons that the patient may visit the investigational site outside of the visit schedule during the course of the study. The site should record any site visit even if unscheduled and document the reason for the visit. For the SRP treatments, there is one required visit within the study procedures, and all additional visits that are required to complete the SRP treatment must be recorded as “unscheduled” SRP visits.

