### 7.6.2 Scaling and Root Planing (SRP)

First SRP will be performed on teeth with PD  $\geq 4$  mm by using Gracey Hand Curettes at V2. The following SRP treatments will be performed and recorded as “unscheduled” SRP visits. SRP treatments of teeth with PD  $< 4$  mm will be performed based on PI’s judgment, at the time he/she finds it necessary. All SRP treatments must be completed within 8 weeks after V2. If additional SRP visits need to be performed because of periodontitis worsening, based on Investigator’s judgement, they will be recorded as unscheduled visits, including the reason for this unplanned SRP.

PD, mobility and BOP before SRP will be measured as per the standard of care treatments at V2. These data will, however, not be reported in the CRF.

The order of SRP should be determined for individual patients. The identification of each tooth treated and the respective time of treatment should be recorded.

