### 8.1 Definitions

#### 8.1.1 Adverse Events

According to ICH Topic E2A (Clinical Safety Data Management: Definitions and Standards for Expedited Reporting [98]), an AE is defined as any untoward medical occurrence in a patient administered an IP or reference product, which does not necessarily have a causal relationship with the IP or reference product. An AE can therefore be any unfavorable and unintended sign (including a clinically significant abnormal laboratory finding), symptom, or disease temporally associated with the use of an IP or reference product, whether or not it is considered related to the IP or reference product.

Any dental condition identified after signature of the ICF, caused by factors other than periodontitis (e.g. cavity, broken tooth) and requiring future treatment/s, will be identified as an AE. Treatment of this condition (e.g. cavity filling, tooth extraction) will be captured in the CRF.

Worsening of the periodontitis parameters after baseline assessments will not be considered as an AE, as dental assessments will capture any worsening of the periodontal condition. Patients experiencing unexpected worsening of the disease, will be treated based on Investigator's judgement, which will be recorded.

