**Confidentiality Statement**

Data and information contained in this document are considered to constitute trade secrets and confidential commercial information, and the legal protections provided to such trade secrets and confidential information are hereby claimed under the applicable provisions of applicable law. No part of this document may be publicly disclosed without the written consent of Philip Morris Products S.A.

		
inflammatory drugs should not be given for more than 6 consecutive days.
 
Reason to change: The distinction between topical and systemic drug was not clearly made, thus has been clarified.

6.7 New section	Concomitant Therapeutic Procedures	
Amended text Concomitant Therapeutic Procedures
 
Any concomitant therapeutic procedure (e.g. tooth extraction due to cavity or due to worsening of periodontitis, appendectomy), which is not part of study procedures (as described in Section 7), will be fully documented in the source document and transcribed into the CRF. All medications used during these concomitant procedures will also be captured in the source document and reported as concomitant medication in the CRF.
 
Reason to change: worsening of periodontitis is not considered as an AE, however, if a tooth is extracted, we need to understand why (e.g. broken tooth or worsening of the disease?). We have thus clarified the fact that the reason for extracting a tooth must be recorded in the CRF.

7	Study procedures	
Old text All study procedures are provided as an overview in the schedule of events (section 15.1, Appendix 1 – Schedule of Events)
 
Amended text All study procedures are provided as an overview in the schedule of events (<del>section 15.1</del>, Appendix 1 – Schedule of Events)
 
Reason to change: wrong reference

7.2	Advice on the Risks of Smoking/Smoking Cessation Advice and Debriefing on IQOS	
Old text will be given to all patients at every visit
 
Amended text will be given to all patients at every <del>v</del>Visit

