1 INTRODUCTION

The purpose of this study is to demonstrate in patients with generalized chronic periodontitis that switching from smoking cigarette to using IQOS improves the response to periodontal therapy and the overall oral health status compared to continuing cigarette smoking.

This Statistical Analysis Plan (SAP) describes the methodology and considerations of the planned analyses and lists the Tables, Figures and Listings (TFLs) for this study. A detailed description of the TFLs will be provided in a separate TFL shell document. Any changes to the TFL shell numbering or to the title of a TFL will not require an amendment to the SAP.

This SAP will be finalized prior to the lock of the clinical database. Any changes to the analyses described in this document or additional analyses performed to supplement the planned analyses, will be documented and described in the clinical study report (CSR).

This SAP has been developed to supplement the statistical analysis described in the clinical study protocol (“P1-OHS-01-JP” final version 4.0 dated 09 Jan 2019). In addition, the SAP has been prepared based on the following documents:

- International Conference on Harmonisation (ICH) E9 guideline entitled, “Guidance for Industry: Statistical Principles for Clinical Trials”
- ICH E3 guideline entitled, “Guidance for Industry: Structure and Content of Clinical Study Reports”
- Case report forms (CRF) final version 3.0.01 (dated 15 August 2018)

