9.1.4 Definitions for Statistical Data Analysis

For periodontal parameters:

Six sites per tooth are to be evaluated. At least 4 of the 6 sites per tooth must be evaluated and have the measurements recorded for the tooth to be included in the assessment. If the site is evaluated and there is no PD to measure, the site must be recorded as 0 to indicate that there was no PD at the site (and to distinguish it from a site that was not evaluated).

When less than 4 sites are recorded, the assessment of the tooth will be considered as missing, and all periodontal assessments for that tooth will be excluded from the calculation of the means over all teeth (see Section 5.1.1).

For BoExp parameters:

Values below the lower limit of quantification (LLOQ) will be imputed using LLOQ/2. For

Confidentiality Statement

Data and information contained in this document are considered to constitute trade secrets and confidential commercial information, and the legal protections provided to such trade secrets and confidential information are hereby claimed under the provisions of applicable law. No part of this document may be publicly disclosed without the written consent of Philip Morris Products S.A.

values above the upper limit of quantification (ULOQ), the ULOQ will be imputed.

The number of values below LLOQ or above ULOQ will be presented in each summary table. If more than 50% of the data are below LLOQ, only the number and percentage of values below LLOQ will be reported in the summary together with the minimum and maximum values.

For calculation of creatinine adjusted BoExp if the denominator is below LLOQ then the ratio will not be calculated and will be tabulated as “Not Calculated” in descriptive summaries and excluded from the main analysis.

For self-reported tobacco or nicotine containing tobacco product use over the duration of the study data:

Only available data will be included in the product use summaries. Overall product exposure groups will be defined based on the data collected from randomization until EOS.

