9.5.2 Secondary Analyses

9.5.2.1 Secondary Analysis

Analysis of Change from Baseline in PD at V3 and CAL at V4 / V3	
Population	: • As Exposed Set
Contents	: The model will include the PD (or CAL) change from baseline as the dependent variable, adjusting for the following covariates; 
 • The statistical model is described in section 9.5.1. Note that “Full mouth PD at V1” will be replaced as “Full mouth CAL at V1”
Target visit	: • V3 (3 Months) for PD • V3 (3 Months) and V4 (6 Months) for CAL
Remarks	: • Statistical tests for PD at V3, CAL and V4 and V3 are performed in a sequential manner as detailed in section 9.1.8. • The same model for the primary analysis will be used with both V3 and V4 data included; PD at 3 months will be reported only if the test for PD between Cigarette User and IQOS User categories at 6 months is significant. • If the test between Cigarette User and IQOS Users Categories for PD is significant at V3, then the model with change from baseline CAL will be fitted with both V3 and V4 data and the test between CC and IQOS for CAL at V4 will be reported. • If the test between Cigarette User and IQOS User categories for CAL at V4 is significant, then the test between Cigarette User and IQOS User Categories for CAL at V3 will be reported.
Sample code	Refer to “ Primary Analysis ”
Output	15.4.7.1 Analysis of Change from Baseline in Pocket Depth (mm) at V3 with Initial Pocket Depth \geq 4 mm - As Exposed Set - 15.4.7.2 Regression Coefficients and Graphical Diagnostics of Analysis of Change from Baseline in Pocket Depth (mm) at V3- As Exposed Set - 15.4.7.3 Analysis of Change from Baseline in Clinical Attachment Level (mm) with Initial Pocket Depth \geq 4 mm - As Exposed Set -

Confidentiality Statement

Data and information contained in this document are considered to constitute trade secrets and confidential commercial information, and the legal protections provided to such trade secrets and confidential information are hereby claimed under the provisions of applicable law. No part of this document may be publicly disclosed without the written consent of Philip Morris Products S.A

Analysis of Change from Baseline in PD at V3 and CAL at V4 / V3

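### Extraction and repeat SRP for worsening periodontitis are recorded, but no SAP table counts either by randomised arm or product-use category

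*Protocol*

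**What the plan says.** **Extraction.** Protocol 6.7 lists "tooth extraction due to cavity or due to worsening of periodontitis" among the concomitant procedures to be documented in the source and transcribed to the CRF. The text of 6.7 asks for full documentation but does not name the reason. The explicit requirement stands only in the Appendix 5 rationale for adding 6.7, which says that "the reason for extracting a tooth must be recorded in the CRF".

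**Repeat SRP.** Protocol 7.6.2 covers additional SRP visits needed because periodontitis worsens: "they will be recorded as unscheduled visits, including the reason for this unplanned SRP". Routine completion visits carry the same unscheduled label. Protocol 4 (Unscheduled visits) says "all additional visits that are required to complete the SRP treatment must be recorded as" unscheduled SRP visits.

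**Adverse events.** Under Protocol 8.1.1, worsening of periodontitis parameters after baseline "will not be considered as an AE, as dental assessments will capture any worsening of the periodontal condition".

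**Reporting.** SAP 1 states that the plan "lists the Tables, Figures and Listings (TFLs) for this study". SAP 9.1.6 restricts data from unscheduled visits to listings. SAP 9.1.4 says that when fewer than 4 sites of a tooth are recorded, "all periodontal assessments for that tooth will be excluded from the calculation of the means over all teeth".

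**The concern.** The trial is meant to substantiate that IQOS improves periodontitis. Losing a tooth to periodontitis, or needing SRP again because the disease got worse, is a plain sign of the opposite in an individual patient. The sponsor amended the protocol so that the reason for an extraction would be known, precisely because worsening is not an AE. The SAP then gives these data no by-group count.

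The AE carve-out rests on the dental examinations showing any worsening. That works for a tooth still in the mouth. Once the tooth is gone it cannot be probed, so at every later visit the worst outcome for it is missing from the PD and CAL summaries. A reader of the report would see mean PD and CAL by group without knowing how many patients in each group lost teeth to the disease or were retreated for it.

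**Working it through.** **1. Is there a by-group count anywhere?** The analysis tables in SAP 9.2 to 9.5.4 and the index in SAP 13.1.1 contain no table of extractions, concomitant procedures or repeat SRP, by randomised arm or by product-use category. The count of such tables is 0.

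**2. Why the rules produce this gap.**
- *AE tables:* Protocol 8.1.1 keeps worsening of periodontitis out. It does make dental conditions from other causes AEs, so the condition behind an extraction for a cavity can appear in the AE tables while an extraction for periodontitis does not.
- *Medication/therapy table (15.2.12.2):* limited to the concomitant-medication category and summarised by ATC levels 1 and 2 (SAP 9.5.4.4). Procedures are coded in MedDRA (Protocol 11.2.2), so an extraction has no place there. Protocol 12.8 promises tabulation of concomitant medications and device events and does not name procedures.
- *Unscheduled visits:* SAP 9.1.6 keeps repeat SRP out of tables. Because routine completion visits share the label, only the recorded reason separates the two.
- *Teeth count:* tabulated at baseline only (SAP 9.3).

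**3. What happens to an extracted tooth.** The SAP does not name this case. By inference from SAP 9.1.4, a missing tooth has no recorded sites and drops out of the means. A tooth lost between V3 and V4 still contributes at V3, and SAP 9.5.2.1 says "The same model for the primary analysis will be used with both V3 and V4 data included". The tooth is therefore missing only from visits after its extraction.

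**4. Partial traces.**

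| Place | What it shows | What it lacks |
|---|---|---|
| Primary-model covariates (SAP 9.5.1.1): time since last SRP, target-tooth extraction counts | Coefficients in 15.4.5.2, or a note in 15.4.5.3 that they were dropped | Counts, reason, non-target teeth; droppable at p > 0.05 |
| Shift tables 15.2.7.4 and 15.2.7.16, heatmap 15.1.9.3 | Falling totals of sites or teeth by group | Cause |
| Listing 15.3.7.8 | Periodontal treatment by patient | Group counts; As Exposed Set only |
| Disposition table 15.2.1.1 | Discontinuation for periodontal surgery, by arm | Extraction and repeat SRP |

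**5. How large could the counts be?** The plan gives no event rate. Its only figure used here is 86 per arm, which reproduces: 64 per arm from Protocol 12.2, and 64 / 0.75 = 85.3, rounded up to 86, or 172 in total. Assume that 1% to 10% of patients lose a tooth to periodontitis.
- Expected per arm: 86 × 0.01 = 0.86 to 86 × 0.10 = 8.6.
- Chance of at least one among 172 at 1%: 1 − 0.99^172 = 0.82.
- Clopper-Pearson 95% intervals: 1/86 gives 0.0% to 6.3%; 4/86 gives 1.3% to 11.5%; 9/86 gives 4.9% to 18.9%.
- Newcombe 95% interval for the difference with equal counts per arm: ±5.2 points at 1 v 1, ±7.3 at 4 v 4, ±9.6 at 9 v 9.

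Some events are likely even at the low end, and the intervals are too wide for comparison. A table would be descriptive.

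**The case against.** The strongest reply is that nothing inferential changes. No test, hypothesis, sample size or decision rule is affected, the data are collected, and SAP 1 allows supplementary analyses documented in the CSR. That is fair and limits the weight of the point. It does not remove it, because the gap follows from stated rules (8.1.1 and 9.1.6), so a report written to plan would leave these counts out.

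A reader might infer that the primary result is biased. The documents do not support that. They give no event rate, no reason to expect the groups to differ, and no statement on whether baseline and V4 sites are matched. As an illustration only, suppose sites are not matched, the lost tooth would have measured 6 to 8 mm, the other diseased sites average 3.0 to 4.5 mm, and the patient had 5 to 10 diseased teeth (all assumed, although Protocol 5.1.1 implies at least 5, being more than 30% of 15). One patient's V4 mean then shifts by (6 − 4.5)/10 = 0.15 mm to (8 − 3)/5 = 1.0 mm. If arms differed by 10 points, the most that a 1% to 10% event range allows even with no events in one arm, the contrast would move by 0.015 to 0.10 mm against the 0.25 mm design difference. If sites are matched, a tooth with no change among teeth improving by 1 mm shifts one patient by 1/10 to 1/5 mm, and the contrast by 0.01 to 0.02 mm.

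A reader might also infer that Listing 15.3.7.8 loses many patients through major deviations. SAP 8.5.1 classes most of these as evaluable, and only an unsigned consent form is explicitly non-evaluable, so that loss is probably small.

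Finally, repeat SRP depends on the investigator's judgement. The trial is open label and only the examiner is blinded, so retreatment counts could reflect knowledge of allocation. This stands, and the table must say so.

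**Conclusion.** The point holds as incomplete harm reporting. Extraction for worsening periodontitis and SRP repeated for worsening are recorded, and neither is counted by randomised arm or product-use category in any planned table. The premise for keeping worsening out of the AEs fails at visits after an extraction, and the existing traces do not supply counts by group with the reason.

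The size is unknown. The expected 0.9 to 8.6 patients per arm rests wholly on an assumed 1% to 10% rate. Two further points are inferences: that an extracted tooth drops out through the under-4-sites rule, and that its reason is reliably in the CRF, since only the Appendix 5 rationale demands it. The table should be added, but its absence does not undermine the primary analysis.

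**What to change.** Add one descriptive Safety Set table to SAP 9.5.4, shown by randomised arm (randomised patients) and by product-use category:

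- number and percentage of patients with teeth extracted after V2, and number of teeth, by recorded cause and split by V1 mobility grade, so that teeth already failing at entry are visible;
- number and percentage of patients, and number of visits, with unplanned SRP whose recorded reason is worsening, kept apart from routine SRP completion;
- number of teeth present at V1, V3 and V4.

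Exempt unplanned SRP from SAP 9.1.6 for this table. Add a footnote that repeat SRP is an investigator decision in an open-label trial.

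**Cost.** One extra table and a one-line exception. Extractions, SRP visits and V1 mobility are already recorded, and procedures are already coded in MedDRA. The randomised-arm split is new for the Safety Set, which the SAP otherwise analyses by actual exposure. The documents do not say whether a need for extraction at V1 is in the CRF, which is why V1 mobility grade is used for the split. Small counts can be over-read, and the rows for other causes overlap in part with dental AEs.

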## 7 STUDY PROCEDURES

Personnel performing or recording study measurements must have appropriate and fully documented training. Quality control (QC) measures must be defined, implemented and documented. All study procedures are provided as an overview in the schedule of events (Appendix 1 – Schedule of Events).

In this section, only the expected/planned time points for the various measurements are given. Considering that not all study participants can have a procedure at the same time point, adequate time windows are given for each study procedure and each time point in section 9. Site personnel will adhere to the site's standard operating procedures (SOPs) for all activities relevant to the quality of the study. Appropriate dental/medical advice will be provided to the patients in case of any dental/medical findings requiring health care.

### 7.1 Informed Consent and Guidance

Prior to any study assessment being performed, the patient will be asked to provide his/her written consent to participate to the study (ICF) section 1.3. All the assessments must start after the time of ICF signature by the patient before study participation. During the consent process, the Investigator or designee obtaining consent must inform each patient of the nature, risks and benefits of, and alternatives to study participation. In addition, each patient must review the ICF and must have sufficient time to understand and have adequate opportunity to ask questions. The ICF must be signed and dated (date and time) prior to undertaking any study-specific procedures. A copy of the signed ICF must be given to the patient.

